10.2.4 Test of Hypothesis

The primary test of hypothesis 1 is a test of the significance on the coefficients on the BSFT term alone from the intercept equation-- γ_{000} , and the term that includes BSFT interacted with a_{ijt} from the equation for the slope of the growth curve-- γ_{001} . If γ_{000} is significantly less than zero, then BSFT participants (on average across all the treatment sites) will have achieved lower drug use immediately post intervention than did the TAU participants. If γ_{001} is significantly less than zero, then BSFT participants (on average across all treatment sites) will have had a decrease in drug use relative to the TAU participants from immediately post-intervention to 12months post intervention. Conversely if γ_{000} and γ_{001} are significantly greater than zero, then BSFT participants will have, respectively, greater drug use immediately post-intervention and greater increase in drug use relative to TAU participants. To simplify the presentation and interpretation of results, planned contrasts will also test if there are differences between BSFT and TAU at each follow-up time point (T4 to T12).

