10.2 Primary Outcome and Hypothesis

Hypothesis 1. BSFT will be significantly more effective than TAU in reducing adolescent drug abuse, defined as the percentage of drug use days in 28-day periods.

Outcome Variable. The outcome variable for this hypothesis is the percentage of days of drug use within a 28-day period. This variable will be constructed from the Timeline-Follow-back instrument and will be measured as the sum of the number of days with positive use in 28-day increments (there are thirteen 28-day periods in this design, B1 and T1-T12). Periods in which the participant is in a restricted environment will be flagged in the database, but will be included in the primary analysis. If there is missing information on the time-line follow-back within a 28-day period, the percentage will be calculated as the percentage of available days in that period, as long as not more than 14 days are missing. There is a chance that data collected at the same assessment point are more related than data collected across assessment points. Our data analysis strategy exploits the nested structure of our data. Thus, in this protocol, 28-day measures of drug use are nested within 13 assessment points, these assessment points are nested within individuals, individuals are nested within community treatment providers. The statistical model, as defined below, accommodates these different nesting factors. From our experience, in models with many levels of nesting, it is not uncommon for some of the random effects associated with these levels to have close to zero variance. Thus, our strategy will be to first examine the trajectories (blind to the condition assignment), and to

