estimate the random effects associated with each level of nesting. If any of these are statistically not significantly different from zero, we will drop these from the specification, prior to testing of the hypotheses. Note further, that as described below, the Hierarchical Linear Model (HLM) to be used to test our hypotheses is described with only a linear term in time. During our examination of the levels of nesting we will also examine the trajectories (again blind to condition) to ascertain any higher order polynomial trends in the data. For example, if a quadratic term in time is found to have significant variance over individuals, we will include the quadratic term in the HLM. The model as presented below does not show the nesting of 28-day periods within assessments and only shows the linear term of the growth model in an effort to keep the notational clutter to a minimum.

Analysis. Hypothesis 1 will be tested using hierarchical linear models (HLM) (Bryk & Raudenbush, 1992) to estimate the growth curve of drug use post-randomization. The trajectory of change in drug use will be compared between BSFT and TAU. HLM controls for the nesting of both repeated observations within the same adolescent over time and the nesting of adolescents within a CTP and further allows for a single test of the effect of the intervention across multiple times and sites (see planned post-hoc tests, below). HLM allows for the flexible inclusion of adolescents who may have missed assessments, and allows for non-linearity of the trajectory of change in the dependent measure. Finally, HLM allows us to consider treatment site as a random effect and to examine variability in treatment effects across sites. The treatment of site as a random effect is in keeping with the mission of the CTN to test the general applicability of proven treatments in real world settings. Thus, it is a goal of this protocol to show that BSFT will be efficacious in the population of community treatment providers, not just the community treatment providers in the sample (which a fixed effect specification would imply). This specification of the test actually compares the effectiveness of BSFT relative to the average effectiveness of TAU in the sites in the protocol. The analysis will include as a covariate referral from an institution for the treatment of drug.

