10.2.6 Planned Post Hoc Analysis

In most hypotheses, HLM has been used to minimize the number of statistical tests per hypothesis. In the case of a significant effect of BSFT in any of these hypotheses, planned post-hoc tests will look at the time path of this difference and document when the simple differences are statistically significant.

An additional sequence of analyses will be done to address variability in the effect of BSFT. This will be accomplished by adding explanatory variables associated with the sites in the equations at Level 3 for the intercept and slope. For example, because TAU services are not standardized, additional planned analyses will be conducted to examine the effectiveness of BSFT compared to various types of TAU services (e.g., individual therapy, group therapy, day treatment, recreational treatment). These analyses will include full exploration of the planned characterization of TAU services at each CTP. These analyses will also examine if there are differential attrition rates in different types of TAU services, and if BSFT is more effective than TAU when controlling for different engagement and retention rates across TAU services. As such, these analyses will help to address the possibility that TAU is just as effective as BSFT for those cases that remain in treatment. In all of these analyses, referral from an institution for the treatment of drug use will be entered as a covariate.

Companion analyses will examine whether patient characteristics, after controlling for TAU differences, are related to effectiveness of the BSFT intervention. These will be accomplished by adding explanatory variables in the equations for Level 2 for the intercept and slope. Variables to be considered include: age, gender, ethnicity/race, level of drug use, primary drug of abuse, family type, and baseline levels of internalizing/externalizing problems, family and peer functioning. This will answer the question of for whom the intervention worked.

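### The primary test of Hypothesis 1 names two coefficients, each with its own conclusion, and gives no rule for combining them, so the type I error of the primary claim is not fixed

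*Protocol*

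**What the plan says.** Hypothesis 1 is a single directional statement: "BSFT will be significantly more effective than TAU in reducing adolescent drug abuse, defined as the percentage of drug use days in 28-day periods". Section 10.2 (Analysis) presents the hierarchical model partly on the ground that it "allows for a single test of the effect of the intervention across multiple times and sites", and section 10.2.6 adds that "HLM has been used to minimize the number of statistical tests per hypothesis".

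Section 10.2.4 then defines the test: "The primary test of hypothesis 1 is a test of the significance on the coefficients on the BSFT term alone from the intercept equation", plus the BSFT-by-time coefficient. Time is centred at T4, so the first is the group difference at T4 and the second is the difference in slope. Each is interpreted separately:

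- If the first is significantly negative, BSFT participants "will have achieved lower drug use immediately post intervention than did the TAU participants".
- If the second is significantly negative, BSFT participants "will have had a decrease in drug use relative to the TAU participants from immediately post-intervention to 12months post intervention".
- If both are significantly positive, the reading is "greater drug use immediately post-intervention and greater increase in drug use relative to TAU participants".

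The section adds contrasts at each follow-up from T4 to T12, as an aid to presenting and interpreting the results. No alpha is assigned to either coefficient. It calls the tested coefficients γ000 and γ001. Section 10.2.3 defines these as the TAU mean at T4 and the TAU rate of change; the BSFT terms there are γ100 and γ101.

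**The concern.** The sentence that decides whether the trial succeeds has several possible outcomes and no verdict for most of them. One coefficient may be significant and the other not. The two may also be significant in opposite directions: lower use at T4 followed by a steeper rise would count for BSFT on the first and against it on the second. The rule could then be chosen after the results are seen, and the error rate depends on which rule is chosen.

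The gap also reaches the follow-up analyses. Section 10.2.6 makes the time-path tests conditional on a significant BSFT effect, and that condition is undefined when the two coefficients disagree. Section 10.4.1 plans power for one effect, so the sample size does not correspond to a two-coefficient test.

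**Working it through.** **Step 1. What the stated power assumes.** Inputs from sections 10.4 and 10.4.1: J = 8 sites, effective n = 57 per site, δ = .45, site variance σ² = .10 (moderate) and .15 (large). The small value cannot be read in the available text; .05 is assumed. The model is a multisite trial with random site effects, tested by F on 1 and J − 1 = 7 df at two-sided .05, with noncentrality λ = Jδ²/(σ² + 4/n). Here Jδ² = 8 × .2025 = 1.62 and 4/57 = .0702.

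| σ² | λ | Power, one 1-df test | Stated |
|---|---|---|---|
| .05 | 1.62/.1202 = 13.48 | 88.1% | 87% |
| .10 | 1.62/.1702 = 9.52 | 75.4% | 75% |
| .15 | 1.62/.2202 = 7.36 | 64.5% | 64% |

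The stated figures are reproduced as one two-sided 5% test. A one-sided test would give 95/87/79%, which does not fit.

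**Step 2. Correlation of the two estimates.** Assume T1 to T12 complete, time centred at T4 (values −3 to 8, mean 2.5, sum of squares about the mean 143) and a random intercept with within-person correlation ρ. Section 10.4.1 assumes ρ = .1 and calls .2 to .4 not uncommon. Up to a common factor:

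- variance of the mean: Vm = ρ + (1 − ρ)/12
- variance of the slope: Vs = (1 − ρ)/143
- correlation of T4 intercept and slope: r = −2.5√Vs / √(Vm + 6.25Vs)

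For ρ = .1: Vm = .175, Vs = .00629, so r = −.198/.463 = −.43. For ρ = .2 and .4, r = −.34 and −.23.

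**Step 3. Type I error under each possible rule.** Each coefficient is tested at |z| > 1.96. With independence, the chance that at least one is significant is 1 − .95² = 9.75%; the upper bound is .05 + .05 = 10%. For other r, bivariate normal probabilities apply. The both-significant rate is 10% minus the either rate.

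| ρ | r | Either suffices, two-sided | Either suffices, favouring BSFT | Both required, two-sided |
|---|---|---|---|---|
| .1 | −.43 | 9.3% | 5.0% | 0.7% |
| .2 | −.34 | 9.4% | 5.0% | 0.6% |
| .4 | −.23 | 9.6% | 5.0% | 0.4% |
| independent estimates | 0 | 9.75% | 4.9% | 0.25% |

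A single two-sided 5% test puts 2.5% in favour of BSFT. A joint test of both coefficients has 5% by construction.

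**Step 4. Power of a joint test.** Put δ = .45 in one coefficient only, with uncorrelated estimates and the same λ, and use F on 2 and 7 df. Power is 75/59/48% against 88/75/65% for the 1-df test, a loss of 13 to 16 points. With 6 denominator df it is 71/56/45%.

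**The case against.** The strongest reply is that section 10.2.4 speaks of a test of coefficients, which can be read as one joint test; the sentences that follow would then only interpret signs. That fits the single-test wording of section 10.2 and the aim stated in section 10.2.6. It stands to this extent: either-suffices is not the only reading, and a reader who infers that the error rate simply is 10% rather than 5% goes further than the document. But a joint reading does not explain why each coefficient has its own significance condition, and no joint statistic is named.

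Other limits also stand:

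- The 9 to 10% counts errors in both directions. Hypothesis 1 is directional, and false claims for BSFT go from 2.5% to about 5%.
- A reader might add the T4 to T12 contrasts and arrive at about 12%. They are offered as presentation aids, so they are not further routes to the primary claim.
- A reader might take the overall .05 in section 13.0 as a limit on the two coefficients together. It concerns an unscheduled interim efficacy analysis and says nothing on this point.
- The correlations in step 2 are person-level. The protocol's model also has random site effects on both BSFT terms. In the power model these supply .05/.1202 = 42% to .15/.2202 = 68% of the treatment-effect variance, and their correlation is unspecified. At |r| = .8 the either-suffices rate falls to 7.8%, which is still above 5%.

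Finally, decision rules are often left to the statistical analysis plan. Here, however, the protocol itself defines the primary test, in a form that does not match its own single-test statement or its power calculation.

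**Conclusion.** The point holds as a defect in the stated primary test. Two coefficients carry separate conclusions without a combination rule, an alpha split or a provision for opposite signs, while the power is that of one test. The type I error of the primary claim therefore ranges from under 1% (both required), through 5% (joint), to about 9 to 10% two-sided, or about 5% in favour of BSFT (either suffices). The outer figures assume two-sided 5% tests, normal theory and the protocol's own within-person correlations of .1 to .4; a strong site-level correlation would move them. The documents do not support 10% as the error rate outright. They support the statement that it is not controlled as written.

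**What to change.** State in section 10.2.4 one primary test at two-sided 5%, in one of two forms:

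1. **Joint test of all BSFT terms in the final model.** This has 2 df if the trajectory is linear, and more if a BSFT-by-quadratic term is kept, as sections 10.2 and 10.2.5 allow. Individual coefficients are tested only after the joint test is significant. With two terms this is a closed procedure; with three, pairwise joint tests would be needed in between. Because a joint test has no direction, a claim of benefit must also require the estimated effect to favour BSFT, using a summary named in advance.
2. **One pre-named 1-df contrast.** This keeps the power basis of section 10.4.1 (87/75/64%) and settles the question of opposite signs.

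The second form costs only wording, but the team must commit to one contrast. The first costs power when the effect lies in one coefficient alone (about 75/59/48% rather than 88/75/65%, on the assumptions in step 4), so power must be restated if it is chosen. Splitting alpha at .025 per coefficient is no cheap way out: single-coefficient power would be about 77/61/49%.

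In the same edit, label the T4 to T12 contrasts as descriptive follow-up, and correct the tested symbols from γ000 and γ001 to γ100 and γ101.

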where y_{ijt} , a_{ijt} , and ε_{ijt} , are % of drug use days, time, and a random (or error) term, respectively, for person i , in CTP j , at observation occasion t . The variable a_{ijt} will be measured as time from assessment point (T4), which occurs four months post randomization. The variables π_{ij0} and π_{ij1} are the intercept and slope of drug use, respectively for person i , in CTP j .

10.2.2 Level 2

The Level 2 model describes the individual intercept, π_{ij0} , and the individual slope term, π_{ij1} as a function of *BSFT*:

Level 2

$$\pi_{ij0} = \beta_{0j0} + \beta_{1j0}BSFT + r_{ij0},$$

$$\pi_{ij1} = \beta_{0j1} + \beta_{1j1}BSFT + r_{ij1}.$$

The *BSFT* variable is a 0-1 or dummy-coded variable that is coded 1 if the participant is receiving BSFT, and 0 otherwise. Given this coding of the *BSFT* variables, β_{0j0} and β_{0j1} are the intercept and slope, respectively, for participants who are in the TAU condition. The parameters, β_{1j0} and β_{1j1} , are the increments to the intercept and slope of the TAU participants, (β_{0j0} and β_{0j1} , respectively), for participants receiving *BSFT* at treatment site j (i.e. intercept for *BSFT*= $\beta_{0j0} + \beta_{1j0}$ and slope for *BSFT*= $\beta_{0j1} + \beta_{1j1}$). Finally, r_{ij0} and r_{ij1} are person-specific random terms for the intercept and slope.

10.2.3 Level 3

The Level 3 model incorporates the variability across treatment sites into the coefficients of the Level 2 model.

Level 3

$$\beta_{0j0} = \gamma_{000} + u_{0j0},$$

$$\beta_{1j0} = \gamma_{100} + u_{1j0},$$

$$\beta_{0j1} = \gamma_{001} + u_{0j1},$$

$$\beta_{1j1} = \gamma_{101} + u_{1j1},$$

At level 3, the u terms are site-specific error terms. In the absence of covariates, γ_{000} is the grand mean of TAU at T4 (immediately post intervention) and $\gamma_{000} + \gamma_{100}$ is the mean of BSFT at T4 and γ_{100} is the treatment effect of BSFT at T4. Again, in the absence of covariates, γ_{001} is the rate of change from T4 to T12 for TAU and $\gamma_{001} + \gamma_{101}$ is the rate of change of BSFT from T4 to T12 and γ_{101} is the treatment effect of BSFT at T4.

Whereas the model to be tested is conceptualized in 3 distinct levels, it is actually estimated as one single equation with multiple fixed and random effects. Substituting in the various equations gives:

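### Section 10.2.4 attaches the symbols γ000 and γ001 to the primary test, but the model defines these as the TAU intercept and slope; the BSFT-TAU contrasts are γ100 and γ101

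*Protocol*

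**What the plan says.** **Model (Protocol 10.2.2, 10.2.3).** The treatment variable is "coded 1 if the participant is receiving BSFT, and 0 otherwise". Without covariates, "γ_{000} is the grand mean of TAU at T4 (immediately post intervention"), "γ_{100} is the treatment effect of BSFT at T4" and "γ_{001} is the rate of change from T4 to T12 for TAU". The BSFT slope is given as γ001 + γ101. The same sentence then ends by saying that "γ_{101} is the treatment effect of BSFT at T4", the label already given to γ100.

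**Primary test (Protocol 10.2.4).** The test is placed on "the coefficients on the BSFT term alone from the intercept equation-- γ_{000", and on the BSFT-by-time term, which is labelled γ001. The decision statements follow on the same two symbols. The first is "If γ_{000} is significantly less than zero, then BSFT participants (on average across all the treatment sites) will have achieved lower drug use" immediately after the intervention. The second reads γ001 below zero as a decline under BSFT relative to TAU. The third reads both symbols above zero as greater use, and a greater increase in use, under BSFT.

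**The concern.** Section 10.2.4 is the one place in the protocol that ties the primary hypothesis to named coefficients and says which sign means benefit and which means harm. If the symbols are followed, the test concerns the TAU arm alone: its level at T4 and its change over time. A falling TAU trajectory would be reported as a BSFT advantage in slope, and a rising one as a BSFT disadvantage.

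A reader who turns to 10.2.3 to settle the matter meets a second wrong label, because γ101 is there called an effect at T4. Section 10.3 analyses hypotheses 2b to 2e by the method used for Hypothesis 1, so the mislabelled rule carries over to them by reference.

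**Working it through.** **1. What each coefficient is.** The combined equation at the end of 10.2.3 has the fixed part

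E[y] = γ000 + γ100·BSFT + γ001·a + γ101·BSFT·a,

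with a = 0 at T4, BSFT = 1 for BSFT and 0 for TAU. Substituting:

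- TAU at T4 (BSFT = 0, a = 0): γ000
- BSFT at T4 (BSFT = 1, a = 0): γ000 + γ100, so the difference at T4 is γ100
- TAU slope: γ001
- BSFT slope: γ001 + γ101, so the difference in slope is γ101

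Neither γ000 nor γ001 contains a between-arm contrast.

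**2. Words against symbols in 10.2.4.**

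| Described in words | Symbol given | Symbol in the model |
|---|---|---|
| BSFT term, intercept equation | γ000 | γ100 |
| BSFT × time, slope equation | γ001 | γ101 |

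γ000 and γ001 each occur three times in 10.2.4 (definition, below-zero rule, above-zero rule). γ100 and γ101 do not occur there, although 10.2.3 prints them. The consistency makes a text-extraction fault unlikely.

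**3. A numerical reading, sampling error ignored.** Take arbitrary values γ000 = 7, γ100 = −3, γ001 = 0.5, γ101 = −0.2. TAU at T4 is 7 and BSFT is 7 − 3 = 4. The TAU slope is 0.5 and the BSFT slope 0.5 − 0.2 = 0.3. BSFT is better on both counts, yet γ000 and γ001 are both positive, which the above-zero clause reads as BSFT worse on both.

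**4. Simulation of the displayed model only.** No covariates, identity link, 8 sites of 60, 12 monthly occasions, 1,000 runs, site-level t test on 7 df. Assumed: SD 20 points; site variance of the effect 0.10 on the standardised scale; TAU mean at T4 25% or 10%; TAU slope −0.5 or +0.5 points per month.

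- γ000 was significantly above zero in 100% of runs whether BSFT was 9 points better, equal or 9 points worse (TAU mean 25%), and with no effect at a TAU mean of 10%.
- γ001 followed the TAU slope: below zero in 100% of runs when TAU declined and BSFT had no effect; above zero in 100% when TAU rose, although BSFT was better.
- With the right symbols, no effect and TAU mean 25%, rejection was 2.3% + 3.3% = 5.6% for γ100 and 2.0% + 2.6% = 4.6% for γ101. With BSFT better by 9 points (9/20 = 0.45 SD), γ100 was significantly below zero in 80.9%.

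**5. The plan's own power figures.** Section 10.4.1 gives 87%, 75% and 64% for J = 8, effective n = 57, effect 0.45. Using noncentrality J·δ²/(σ² + 4/n) on 1 and J − 1 df, two-sided α = 0.05 (assumed), with J·δ² = 8 × 0.2025 = 1.62 and 4/57 = 0.0702:

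- σ² = 0.05 (assumed for small; not legible in the text): 1.62/0.1202 = 13.5, power 88.1%
- σ² = 0.10: 1.62/0.1702 = 9.5, power 75.4%
- σ² = 0.15: 1.62/0.2202 = 7.4, power 64.5%

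These agree to within about one point. The calculation concerns a between-arm effect, so correcting the subscripts leaves it unchanged.

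**The case against.** The strongest reply is that no careful analyst would be misled. The sentence that introduces the symbols names the coefficients in words, and in the combined equation only γ100 and γ101 fit that description. Section 10.2 says that the trajectories of the two arms are compared, 10.2.3 correctly calls γ100 the effect at T4, and 10.2.4 adds BSFT-TAU contrasts at each time from T4 to T12 that carry no wrong symbol. The γ101 label can also be corrected from its own sentence, which makes γ001 + γ101 the BSFT slope. All of this stands, and it makes the error recoverable. It does not make the written rule right: the added contrasts are offered to ease presentation and do not replace the primary test.

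A reader might go further and infer that BSFT could never be declared better, or that the rule reports harm with probability near 1 whatever the true effect. The documents do not support that in general. The reading of γ000 as the TAU mean is given only for a model without covariates. Sections 10.1.1, 10.2 and 10.2.1 plan many: baseline drug use, the urn factors, age, gender, comorbidity, primary drug, family variables and referral source. γ000 is then the TAU intercept with every covariate at zero, that is, the TAU mean minus the sum of each coefficient times its covariate mean. No centring of covariates is specified, so it can be negative. Section 10.2 also allows a Poisson link, under which γ000 is on the log scale and zero is no floor. The simulation above does not extend to those models. In them γ000 is still not a treatment contrast.

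**Conclusion.** The point holds as an internal contradiction in the stated primary decision rule. Section 10.2.4 disagrees with its own verbal description, with the definitions in 10.2.2 and 10.2.3, and with the combined equation. Taken literally, all six symbol uses point to TAU parameters. The label of γ101 in 10.2.3 is a second, smaller slip.

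The size is limited. The intended tests, γ100 and γ101, are clear from the words, and the design, sample size and power do not change. That γ000 cannot be negative holds only for the displayed model without covariates and with an identity link; it is not a statement about the planned adjusted analysis. The finding itself rests on the protocol's equations and needs no assumed figure. Only the protocol was available, so a separate analysis plan may already carry the right symbols. The protocol text would still need correcting, because it fixes which coefficients and signs decide the primary hypothesis.

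**What to change.** In Protocol 10.2.4 replace γ000 by γ100 and γ001 by γ101 at every occurrence, three each. In 10.2.3 change the last clause on γ101 to say that it is the difference in slope between BSFT and TAU. Hypotheses 2b to 2e are then corrected by reference.

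The cost is wording only. No change to the model, data collection, sample size or power is needed.

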- Assessment of primary outcomes (drug use) will be conducted at baseline and monthly post-randomization (T1-T12). Secondary outcomes will be conducted at four time points: baseline, 4-, 8-, and 12-months post-randomization.

3.1 Design:

- Randomized “intent to treat” design.
- Informed assent will be obtained from adolescents (ages 12 to 17 inclusive) and consent from a parent or legally authorized guardian. Consent from the guardian will include the adult’s agreement to participate in research, consent for the adolescent to participate in the research study, and consent for any other minors under the age of assent. Additional adults and minors in the family will also be consented/assented prior to participation in any aspect of the study.
- Following consent, participants (adolescent, parents, and family members) will complete a baseline assessment (B1).
- Following the baseline assessment (B1), participants will be randomly assigned to BSFT or TAU.
- Treatment in both conditions will be provided in non-restrictive, community settings (e.g., clinic, home, and school). BSFT consists of 12 to 16 sessions (each approximately 1 to 1.5 hours long) over a 4-month period, plus up to 8 “booster” sessions. TAU will vary depending on the current activities at participating CTPs. For the purpose of this study, it is recommended that TAU in participating CTPs consist of at least 1 therapy session per week and may include participation in ancillary services (e.g., case management, AA, etc.) for a minimum of 3 to 4 months.
- Follow-up assessments of primary outcomes (drug use) will be conducted at monthly intervals following randomization (T1-T12).
- Follow-up assessments for secondary outcomes will be conducted at 4-, 8-, and 12-months following randomization.
- Measures of service utilization (including attendance in study intervention sessions) and adverse events will be conducted at 2-, 4-, 8-, and 12-months post-randomization.
- Alliance with therapist will be assessed 2- and 4-months post-randomization.
- AEs and SAEs will be reported whenever they are identified.

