HLM conceptualizes the growth curve as separate equations for the intercept and another equation or other equations (if more than linear change is examined) for the slope, though both (all) are estimated jointly. With the addition of treatment site as a random effect, this model is a three level HLM model. These three levels are associated with 1) time, 2) individual and 3) site. There is an additional level, or random effect associated with the nesting of 28-day periods within an assessment. As noted above, prior to testing hypotheses, in an analysis blind to condition, we will fit these 4 different levels (and additional polynomial terms). If any of the random components, or polynomial terms are not significantly different from zero, we will drop them from the model. Note that in the presentation that follows, we just present the substantive levels of the individual and omit the higher order polynomial terms to focus the exposition on the substantive issues (the growth curve and site variation). To facilitate interpretation of the growth curve, time will be centered on the 4-month post-randomization assessment (T4). Thus, the intercept term represents the difference between the two conditions immediately post intervention. If the expected ordinal nature of the outcome measure results in sufficient deviation from normality a Poisson link function will be used.

10.2.1 Level 1

For Hypothesis 1, the time path of percentage of days having used drugs in 28-day periods will be estimated and the growth trajectory will be parameterized to be a function of BSFT intervention status. Additional predictors will be the stratification variables specified in the urn randomization and the other variables, described under the heading randomization (see section 10.1.1) and any baseline variables found to predict the occurrence of missing data. The growth curve analysis will include the times after baseline only, and baseline value of the dependent measure will be included as a covariate (i.e. an analysis of covariance parameterization). The presentation below does not include the baseline value of drug use or

these other additional covariates, to ease the exposition. As mentioned this is a three-level HLM model. Level 1 describes the trajectory over time for an individual participant:

Level 1

$$y_{ijt} = \pi_{ij0} + \pi_{ij1} \cdot a_{ijt} + \varepsilon_{ijt},$$

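### Hypothesis 1: the slope is fitted to T1–T12 but interpreted as post-intervention change from T4 to T12, which centring time at T4 does not deliver

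*Protocol*

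**What the plan says.** Section 10.2 (Analysis) uses a hierarchical linear model "to estimate the growth curve of drug use post-randomization". Section 10.2.1 fixes the time span: "The growth curve analysis will include the times after baseline only, and baseline value of the dependent measure will be included as a covariate". The primary outcome is assessed monthly from T1 to T12 (section 3.1), so twelve periods enter the curve. Time is centred at T4, and section 10.2 states that "the intercept term represents the difference between the two conditions immediately post intervention". The displayed model (10.2.1 to 10.2.3) has one slope per person, with no break at T4.

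The slope is nevertheless given a narrower meaning. Section 10.2.3 says that "γ_{001} is the rate of change from T4 to T12 for TAU" and describes the BSFT slope over the same window. Section 10.2.4 then reads a negative BSFT slope term as meaning that BSFT participants "will have had a decrease in drug use relative to the TAU participants from immediately post-intervention to 12months post intervention".

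Three further statements matter. BSFT runs over about four months (3.1, 5.1). Higher-order time trends will be examined blind to condition and added if supported (10.2, 10.2.5). Arm contrasts at each time point from T4 to T12 are planned in addition to the two coefficients (10.2.4).

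**The concern.** The period a slope describes is set by the observations that enter the fit, not by where time zero is placed. With T1–T12 in the model, change during treatment and change after it both feed one coefficient, which is then reported as post-intervention change. The same misfit affects the intercept, because the fitted value at T4 is borrowed from the whole line.

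At stake are the two conclusions that 10.2.4 draws: how large the difference is at the end of treatment, and whether it later grows, holds or fades. An effect that was gained during treatment and then simply held could be reported as still growing, or a fading effect as stable.

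The end point is also misnamed. T12 is 12 months after randomization, and section 7.6 places it roughly 8 months after BSFT is completed, so it cannot be 12 months post-intervention.

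**Working it through.** **The plan's own figure.** The only figures for the overall effect are the powers in section 10.4.1: 87%, 75% and 64% with 8 sites, an effective 57 per site and an effect size of 0.45. With non-centrality λ = Jδ²/(σ² + 4/n), a non-central F on 1 and 7 df, two-sided 5% (assumed) and σ² = 0.05 (assumed for small), 0.10 and 0.15, I get 88.1%, 75.4% and 64.5%. These agree within 2 points. They do not depend on how time is specified, so they neither support nor undermine the slope reading.

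**Inputs for the slope check.** Periods t = 1,…,12 and time a = t − 4 come from the protocol. The protocol gives no expected trajectory, so the curves for the arm difference y(t) are assumptions. They are scaled so that the true difference at T4 is 1, with benefit positive. Data are taken as complete and equally spaced; a random intercept-and-slope GLS fit, run on curve A, gave the same coefficients as least squares.

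**Linear fit.** Slope b₁ = Σ(t − 6.5)y / Σ(t − 6.5)², with denominator 143. Fitted T4 difference b₀ = ȳ − 2.5·b₁, since a has mean 2.5. Fitted T4–T12 change = 8·b₁.

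- Curve A builds linearly to T4, then holds. ȳ = 10.5/12 = 0.875 and the numerator is 7.25, so b₁ = 7.25/143 = 0.0507 and b₀ = 0.875 − 0.127 = 0.748. Fitted T4–T12 change +0.41; truth 0.
- Curve B builds to T4, then loses half by T12. ȳ = 8.25/12 = 0.6875 and the numerator is 0.125, so b₁ = 0.0009 and b₀ = 0.685. Fitted change about +0.01; truth −0.50.
- Curve C builds to T4, then loses everything by T12. ȳ = 6/12 = 0.5 and the numerator is −7.0, so b₁ = −0.049 and b₀ = 0.622. Fitted change −0.39; truth −1.00.
- Difference constant from T1, or linear throughout: both coefficients are exact.

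**With a quadratic term and its BSFT interaction.** The coefficient on BSFT × a is now the tangent at T4. The T4–T12 change is 8·b₁ + 64·b₂.

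| Curve | Fitted T4 difference | Tangent at T4, per month | True T4–T12 slope, per month | Quadratic T4–T12 contrast | True T4–T12 change |
|---|---|---|---|---|---|
| A | 0.83 | +0.118 | 0 | +0.08 | 0 |
| B | 0.78 | +0.085 | −0.0625 | −0.40 | −0.50 |
| C | 0.74 | +0.052 | −0.125 | −0.88 | −1.00 |

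So the quadratic model contains nearly the right answer in its T4-to-T12 contrast, but the coefficient that 10.2.4 tests does not show it. In curves B and C that coefficient has the wrong sign.

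**Knot at T4.** A model with separate slopes for T1–T4 and T4–T12 recovers the true T4 difference and later slope in every curve above.

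**The case against.** A reader might infer that the plan forces a single straight line and therefore biases both primary coefficients. The protocol does not support that.

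- Sections 10.2 and 10.2.5 say that only the linear term is displayed, that polynomial trends will be examined, and that quadratic trends will be modelled if there is evidence for them. Significant variance over individuals is offered as an example of a trigger, not as the only one.
- The bias is conditional. It vanishes if the arm difference is constant or linear over T1–T12. With no arm difference at any time, both coefficients are zero, so the mismatch does not create false superiority under that null.
- The T4–T12 contrasts in 10.2.4, and the time-path tests in 10.2.6 if the effect is significant, would reveal much of a fade if a quadratic is retained, as the table shows.
- A break exactly at T4 is not established. Up to 8 booster sessions may follow and length of service varies by case (5.2.1), section 8.3 refers to treatment in the first six months, and TAU may taper over the year (5.2.2). If the difference builds to T6 and then holds (an assumption), a T4-knot model puts the T4 effect at 120% of truth against 91% for the straight line, although its later slope is closer.

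All four points stand as limits on the claim. They do not remove it. Terms are chosen blind to condition, so curvature present only in the arm difference can be missed. If a quadratic is kept, the tested coefficient is a tangent. The contrasts are additional to the primary test and, if computed from a linear model, inherit its misfit. Nor is this a detail left for an analysis plan: the protocol itself states both the model and the interpretation.

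**Conclusion.** The mismatch between fitted span and stated meaning is certain from the protocol's own text. It concerns Hypothesis 1 only: the outcomes of 2b to 2e are measured after baseline at T4, T8 and T12 (10.3), so for them T4–T12 is the fitted span.

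The size is conditional. A linear fit recovers 75% of the T4 effect and adds a false gain of 41% of it if the difference builds to T4 and holds; it recovers 69% and hides the fade if half is lost by T12. These figures rest on assumed curves with a sharp turn at T4, complete data and no retained polynomial term. They illustrate what can happen and do not predict this trial. It would go too far to say that the primary coefficients are biased whatever the data, or that a fade would necessarily go unseen. What holds is that the two tested coefficients carry the meaning given in 10.2.3 and 10.2.4 only if the arm difference is linear over all of T1–T12.

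**What to change.** In 10.2.4, define the post-intervention effect as an explicit model-based arm contrast, T12 minus T4, reported alongside the T4 contrast. Take both from a time specification that lets the arm difference change pace: BSFT interactions with every retained polynomial term, categorical time, or a knot at T4. Because the documents do not establish a clean break at T4, any of the three is defensible; the choice should be fixed before unblinding.

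The minimum repair is to wording: describe the slope as the average trend over T1–T12 and do not interpret it as post-intervention change. Either way, replace the end point in 10.2.4 with 12 months post-randomization, about 8 months post-intervention. In the same edit, align the coefficient labels: 10.2.4 names γ₀₀₀ and γ₀₀₁, whereas 10.2.3 makes γ₁₀₀ and γ₁₀₁ the treatment terms.

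No new data are needed. The cost is precision. For a knot model relative to the line, the standard error of the later slope rises by about 47%, and that of the T4 difference by about 60%, with independent residuals. With assumed person-level variances (intercept 1, slope 0.005 to 0.02, residual 1) the rises are about 14–29% and 8%.
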